# 11. Over the past 3 months:

	YES	NO
Have you felt that you should cut down on your drinking or recreational drug use?	1	0
Have people annoyed you by criticizing your drinking or recreational drug use?	1	0
Have you felt guilty about your drinking or recreational drug use?	1	0
Have you had a drink or taken recreational drugs first thing in the morning?	1	0

12. Are you currently enroll ☐ Yes ☐ No	ed in a clinical trial for migraine?
-	ily diary that is to be completed every day and takes about 5 minutes to ng to complete a daily diary?
-	days when other questionnaires will be asked, and it may take up to 45 re you willing to continue with participation?

# 13 APPENDIX B - HEALTH AND DEMOGRAPHIC QUESTIONNAIRE

We will use your answers to these questions to describe the sample of people living with migraine who participated in this study. This information will also allow us to better understand how this study relates to the broader population of people living with migraine.

There are 22 questions, but some questions have multiple parts. This survey should take about 10 minutes to fill out.

		ease read each question carefully. eck the box next to your answer or fill in the requested information for each question.
Th	e fo	llowing questions are about you.
	1.	What is your current age?
		years old [DROP DOWN]
	2.	How old were you when you were first told by a doctor or other health care provider that you have migraine?
		years old [DROP DOWN] plus an option "I don't remember"
	3.	In the last 4 weeks , how many days did you have headache of any kind (including migraine)?  days with headache (including migraine) [DROP DOWN]
	4.	In the last 4 weeks , how many days were you completely free of headache of any kind (including migraine)?  days free of headache (including migraine) [DROP DOWN]
	5.	Over the past year , have you taken medication(s) to treat your migraine headaches when they happen? (These may be over-the-counter or prescription).
		

☐ Yes [Continue to Question 6]

☐ No [Continue to Question 7]

	6.	What medication(s) have you taken within the past year to treat your migraine headaches when they happen ? (select all that apply)  \[ \textsim \text{Acetaminophen (generic)}
		☐ Acetaminophen, aspirin, caffeine (generic)
		☐ Acetaminophen with codeine (generic)
		

□ Advil (ibuprofen)

□ Aleve (naproxen sodium)

		☐ Almotriptan (generic)
		☐ Amerge (naratriptan)
		☐ Anaprox (naproxen)
		☐ Ansaid (flurbiprofen)

	Aspirin
	Axert (almotriptan)
	Butorphanol tartrate (generic)
	Cambia (diclofenac)
	Cataflam (diclofenac)
	Celebrex (celecoxib)
	Celecoxib (generic)
	Compazine (prochlorperazine)
	Darvocet (acetaminophen and propoxyphene)
	Darvon (propoxyphene+ aspirin+ caffeine)
	Demerol (meperidine)
	DHE-45 injection (dihydroergotamine)
	Diclofenac (generic)
	Dihydroergotamine (generic)
	Duradrin (Isometheptene+ dichloralphenazone+ acetaminophen)
	Eletriptan (generic)
	Esgic (butalbital+ caffeine+ acetaminophen) with or without codeine
	Etodolac (generic)
	Excedrin (acetaminophen+ aspirin+ caffeine)
	Excedrin "Generic" (acetaminophen+ aspirin+ caffeine)
	Excedrin Migraine (acetaminophen+ aspirin+ caffeine)
	Fioricet (butalbital+ caffeine+ acetaminophen) with or without codeine
	Fiorinal (butalbital+ caffeine+ aspirin) with or without codeine
	Flurbiprofen (generic)
	Frova (frovatriptan)
	Frovatriptan (generic)
	Hydrocodone with or without acetaminophen (generic)
	buprofen (generic)
	mitrex (sumatriptan) nasal spray
	mitrex (sumatriptan) pills or tablets/capsules
	Indocin (indomethacin)
	Indomethacin (generic)
	Ketoprofen (generic)
	Ketorolac (generic)
	Lasmiditan (generic)
	Lidocaine nasal spray
	Lodine (etodolac)
	Maxalt (rizatriptan)
	Meclofenamate (generic)
	Meclomen (meclofenamate)
	Meloxicam (generic)
	Meperidine (generic)
	Metoclopramide (generic)
	Midrin (Isometheptene+ dichloralphenazone+ acetaminophen)
$\Box$ /	Migranal nasal spray (dihydorergotamine)

	Mobic (meloxicam)
	Motrin (including prescription Motrin) (ibuprofen)
	Nabumetone (generic)
	Naprosyn (naproxen)
	Naproxen (generic)
	Naproxen sodium (generic)
	Naratriptan (generic)
	Nasal spray (non-prescription) Please specify:
	Nurtec (rimegepant)
	Orudis/ Oruvail (ketoprofen)
	Oxycodone (generic)
	Percocet, Percodan (oxycodone)
	Phenergan (promethazine)
	Phrenilin or Phrenilin Forte (butalbital+ acetaminophen)
	Prochlorperazine (generic)
	Promethazine (generic)
	Reglan (metoclopramide)
	Relafen (nabumetone)
	Relpax (eletriptan)
	Reyvow (lasmiditan)
	Rimegepant (Nurtec)
	Rizatriptan (generic)
	Roxicodone (oxycodone)
	Sinus or allergy medications (e.g., Tylenol Sinus)
	Stadol (butorphanol tartrate)
	Sumatriptan (generic)
	Toradol (ketorolac)
	Tramadol compound (generic)
	Treximet (sumatriptan + naproxen sodium)
	Tylenol (acetaminophen)
	Tylenol with codeine
	Ubrelvy (ubrogepant)
	Ultram, Ultracet (tramadol compound)
	Vanquish (acetaminophen+ aspirin+ caffeine medication)
	Vicodin (acetaminophen and hydrocodone or other hydrocodone compound)
	Voltaren (diclofenac) pills or tablets/capsules
	Voltaren (diclofenac) topical gel
	Zolmitriptan (generic)
	Zomig (zolmitriptan) pills or tablets/capsules
	Zomig (zolmitriptan) nasal spray
	Other prescription injection Please specify
	Other prescription medication (pills or tablets/capsules) Please specify
	Other prescription nasal spray Please specify
$\sqcup$	Other prescription topical Please specify

7.	Do you currently take any medication(s) or receive any treatment(s) to prevent or reduce the frequency or severity of migraine (i.e., preventive medication)?  \[ \to \text{ Yes [Continue to Question 8]} \] \[ \to \text{ No [Continue to Question 9]}
8.	What medication(s) do you take or what treatment(s) do you receive to prevent or reduce the frequency or severity of migraine (i.e., preventive medication)? (select all that apply)
	☐ Acetazolamide (generic)
	☐ Aimovig (erenumab)
	☐ Ajovy (fremanezumab)
	☐ Amitriptyline (generic)
	□ Aspirin
	☐ Atacand (candesartan)
	☐ Atenolol (generic)
	□ Blocadren (timolol)
	☐ Botox (onabotulinumtoxin A)
	☐ Calan/Covera-HS/Isoptin, Verelan (verapamil)
	☐ Candesartan (generic)
	☐ Clopidogrel (generic)
	☐ Coenyzme Q10
	□ Corgard (nadolol)
	□ Cymbalta (duloxetine)
	☐ Cyproheptadine (generic)
	☐ Depakote (divalproex sodium)
	☐ Desvenlafaxine (generic)
	☐ Diamox (acetazolamide)
	☐ Divalproex sodium (generic)
	☐ Duloxetine (generic)
	☐ Dysport (abotulinumtoxinA)
	☐ Effexor (venlafaxine)
	☐ Elavil (amitriptylline)
	☐ Emgality (galcanezumab)
	☐ Escitalopram oxalate (generic)
	☐ Fluoxetine (generic)
	☐ Gabapentin (generic)
	☐ Inderal (propranolol)
	☐ Lacosamide (generic)
	☐ Lexapro (escitalopram oxalate)
	☐ Lisinopril (generic)
	☐ Lopressor (metoprolol)
	☐ Lyrica (pregabalin)
	☐ Magnesium
	☐ Memantine (generic)
	☐ Metoprolol (generic)
	□ Nadolol (generic)

☐ Namenda (memantine)
☐ Neurontin (gabapentin)
☐ Nifedipine (generic)
☐ Nortriptyline (generic)
☐ Nurtec (rimegepant)
☐ Onabotulinumtoxin A (generic)
☐ Pamelor (nortriptylline)
☐ Paroxetine (generic)
☐ Paxil (paroxetine)
☐ Periactin (cyproheptadine)
☐ Plavix (clopidogrel)
☐ Pregabalin (generic)
☐ Prinivil (lisinopril)
☐ Pristiq (desvenlafaxine)
☐ Procardia (nifedipine)
☐ Propranolol (generic)
☐ Prozac (fluoxetine)
☐ Qudexy (topiramate)
☐ Riboflavin (vitamin B2)
☐ Rimegepant (Nurtec)
☐ Sertraline (generic)
☐ Tenormin (atenolol)
☐ Timolol (generic)
☐ Tizanidine (generic)
☐ Topamax (topiramate)
☐ Topiramate (generic)
☐ Toprol XL (metoprolol)
☐ Trokendi (topiramate)
☐ Venlafaxine (generic)
☐ Verapamil (generic)

☐ Vimpat (lacosamide)

☐ Vitamin B2

☐ Vyepti (eptinezumab)

☐ Zanaflex (tizanidine)

☐ Zestril (lisinopril)
☐ Zestrit (tisinoprit) ☐ Zoloft (sertraline)
☐ Other Please specify

☐ Trimipramine (Surmontil)

9.	Do you currently use any of the following medications for any reason , including for your migraine?
	(Select any that apply)
	$\square$ No, I don't currently use any of these medications
	☐ Amitriptyline (Elavil, Vanatrip)
	☐ Amoxapine (Asendin)
	☐ Clomipramine (Anafranil)
	☐ Desipramine (Normpramin)
	☐ Divalproex sodium (Depakote)
	☐ Doxepin (Sinequan)
	□ Eletriptan (Relpax)
	☐ Imipramine (Tofranil)
	☐ Lasmiditan (Reyvow)
	☐ Nortriptyline (Pamelor, Aventyl Hydrochloride)
	☐ Protriptyline (Vivactil)
	☐ Topiramate (Topamax, Trokendi XR, Qudexy XR, Topiragen)

10. What sex were you assigned at birth? (select one only)  □ Male
□ Mate □ Female
☐ Other (please share if you would like):
□ Prefer not to answer
Trefer flot to answer
11. What is your gender? (select one only)
□ Woman
□ Man
☐ Trans Woman
☐ Trans Man
☐ Genderqueer/ Gender Non-Binary
☐ Other (please share if you would like):
☐ Prefer not to answer
12. Are you of Hispanic, Latino, or Spanish origin? (select one only) 
☐ Yes (Optional: How would you describe yourself?)
□ No
☐ Prefer not to answer
13. What race best describes you? (select all that apply) 
☐ American Indian or Alaska Native
☐ Asian
☐ Black or African American
☐ Native Hawaiian or Other Pacific Islander
□ White
☐ Other (please specify):
☐ Prefer not to answer
□ Frerei not to answer
14. What language do you speak most of the time at home? (select one only)
□ English
☐ Another language
Please specify
15. Are you currently married or living with a domestic partner or significant other?
□ Yes
□ No
16 Other than varietals have many adulta live in your barrahald?
16. Other than yourself, how many adults live in your household? [DROP DOWN]

<sup>1 Categories have been selected to conform with federal requirements for the collection and reporting of race and ethnicity data in clinical research, as described in the NIH policy guidelines at: https://grants.nih.gov/grants/funding/women\_min/guidelines.htm

17. How many children live (part-time or full-time) in your household? [DROP DOWN]
18. How would describe how much education you have completed ? [DROP DOWN]
19. How would you describe your current employment status? (select all that apply)  ☐ Student ☐ Employed for wages or self-employed (full time or part time)
Approximate number of hours worked per week: [DROP DOWN]
☐ Not currently employed and looking for work
☐ Not currently employed and not looking for work
☐ Homemaker
☐ Retired
☐ Disabled (or on disability or leave of absence)
☐ Other, please specify
☐ Prefer not to answer
20. Which of these income categories comes closest to the total yearly income for your household, from
all sources? (select one only)
□ Under \$30,000 □ \$30,000 to \$50,000
□ \$30,000 to \$59,999
□ \$60,000 to \$90,000
☐ More than \$90,000
☐ Prefer not to answer

### 14 APPENDIX C - MICOAS DAILY ASSESSMENT (MICOAS DA)

NOTE: For ease of review, items seen at every administration are presented in **bold**. Items seen based on participant responses/conditional logic are presented in *italics*.

ln '	the past 24 hours
1.	Did you have a good day?  ☐ Yes ☐ No
2.	Did you have a migraine day?  ☐ Yes ☐ No
3.	Did you have a headache or head pain?  □ Did not have □ Mild □ Moderate □ Severe
	3.1 How long did the headache last? [if #3 >= Mild] 30 minutes or less More than 30 minutes but 2 hours or less More than 2 hours but less than 4 hours 4 hours or more
	3.2 Did your head pain get worse with activity [if #3 >= Mild]  ☐ Yes ☐ No
	3.3 Did you have throbbing/pounding head pain? [if #3 >= Mild]  ☐ Yes ☐ No
	3.4 Did you have pain only or worse on one side of your head? [if #3 >= Mild]  ☐ Yes ☐ No
	3.5 Did you take any medication to alleviate your head pain? [if #3 >= Mild]  ☐ Yes ☐ No
	3.6 Did you seek care from a health care provider today because of your headache or head pain? [if #3 >= Mild]  ☐ Yes ☐ No
4	Did you experience any of the following? (check all that apply)  Aura (e.g., visual spots or flashes of light, skin tingling or numbness) [if yes, present 4.1]  Dizziness or vertigo [if yes, present 4.2]  Mental Slowness or Fogginess [if yes, present 4.3]  Nausea [if yes, present 4.4]  Neck Pain [if yes, present 4.5]  Sensitivity to Light [if yes, present 4.6]  Sensitivity to Sound [if yes, present 4.7]  Tired [if yes, present 4.8]  Vomiting [if yes, present 4.9]  None of the above [unavailable to select if any other response is selected; if selected go to #5]

[If YES to corresponding response to #4 present 1 item per screen]

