#### 8.1.2 MiCOAS Daily Assessment (MiCOAS DA)

The MiCOAS-DA is a *de novo* assessment intended to be completed by participants on a daily (calendar day) basis. The content of the items is spread across 2 general item and 3 individual measures:

- Symptoms (10 items)
- Subjective Mental Acuity (5 items; includes 1 symptom item)
- Physical Function (7 items)

The MiCOAS-DA also includes two general items asking about the participants day with respect to their experience. These two items ("Did you have a migraine day?" and "Did you have a good day?") of the MiCOAS DA use a Yes/No response scale. Nine of the symptom items use a 4-category ordinal response scale, with verbal labels (0 = Did not have to 3 = Severe verbal labels). One symptom item asks which symptom experienced was most bothersome. The remaining 11 non-symptom items use 5-category ordinal response scales, with verbal labels varying depending on item content. Most symptom items use a severity response scale (0 = Did not have to 4 = Severe verbal labels) while the non-symptom mental acuity and function items use a difficulty response scale (verbal labels ranging from 0= Not at all difficult to 4 = Unable to do).

Additionally, MMDs is a common outcome in preventive migraine trials, several other symptom and symptom-related items not included in the MiCOAS-DA based on relevance/importance to patients, such as duration of

head pain, medication use, and unilaterality of pain, are also included in the DA to allow for the identification of a migraine day and, when summarized, the calculation of MMDs.

A copy of the MiCOAS DA items can be found in Appendix C.

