### 8.1.10 Monthly Migraine Days

MMD is the number of "migraine days" over the selected 28-day periods. It will be calculated when at least 15 days of the diary are completed out of each 28-day period (through Week 4, Week 5, Day 1 through Week 8). If the number of missing days in the respective 28-day period is > 15 days, MMD will be coded as missing. When the number of missing days in the respective 28-day period is between 1 and 14, a normalization procedure will be applied by multiplying the proportion of migraine days (number of migraine days divided by total number of non-missing days) by 28. For example, if a subject reports 5 migraine days over a total of 20 non-missing diary days, the normalized MMD value would be 7 (i.e., (5/20)\*28 = 7).

The definition of a migraine day will be adapted from the International Headache Society International Classification of Headache Disorders-3 criteria of migraine and current FDA draft guidance (FDA, 2023). Specifically, a qualified migraine day is defined as any calendar day with a headache (head pain of mild, moderate, or severe intensity), with or without aura, lasting for  $\geq$  30 minutes and meeting either of the following criteria (A or B):

- A.  $\geq 2$  of the following headache characteristics:
  - a. Unilateral location
  - b. Pulsating quality (throbbing),
  - c. Moderate or severe pain intensity,
  - d. Aggravation by or causing avoidance of routine physical activity (e.g., walking to climbing stairs)
- B.  $\geq$  1 of the following:
  - a. Nausea and/or vomiting,
  - b. Photophobia
  - c. Phonophobia

Additionally, the use of acute migraine medications to treat head pain of any duration will also be considered a qualified migraine day.

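### Diary item 3.2 does not collect the avoidance part of migraine-day feature A(d), so monthly migraine days cannot be scored exactly as Section 8.1.10 defines them (minor)

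*Protocol*

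**What the plan says.** Section 8.1.10 counts a calendar day as a migraine day if a headache lasts at least 30 minutes and meets a feature rule, "meeting either of the following criteria (A or B"). Criterion A needs two of four headache characteristics. The fourth, A(d), has two parts joined by an or: "Aggravation by or causing avoidance of routine physical activity (e.g., walking to climbing stairs"). Criterion B needs one of nausea and/or vomiting, photophobia, or phonophobia. There is also a separate route: "the use of acute migraine medications to treat head pain of any duration will also be considered a qualified migraine day".

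Section 8.1.2 says that several items outside the MiCOAS-DA measures "are also included in the DA to allow for the identification of a migraine day" and the calculation of MMD. Those items are in Appendix C. The one for A(d) is item 3.2, a Yes/No question shown when head pain is at least mild: "Did your head pain get worse with activity".

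Section 5.2 chose the study duration so that MMD could be calculated and used as a reference variable.

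**The concern.** The definition and the instrument do not match, in two ways.

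- **Avoidance is not asked.** A participant who rested because of the headache, and whose pain therefore did not worsen, can truthfully answer No to item 3.2 and still meet A(d).
- **Routine is not specified.** A participant whose pain worsened only during strenuous exercise can truthfully answer Yes, although A(d) refers to routine activity. The protocol's own screener (Appendix A, item 7) does tie worsening to routine activities, with walking and stairs as examples.

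A later analysis plan cannot repair the first gap, because avoidance that was never asked about cannot be recovered. At stake is whether MMD, one of the reference variables for validation, is the quantity that Section 8.1.10 says it is.

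**Working it through.** **1. Match each feature to its diary item (Section 8.1.10 against Appendix C).**

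| Feature | Diary item | Match |
|---|---|---|
| A(a) unilateral | 3.4, "Did you have pain only or worse on one side of your head" | collected |
| A(b) pulsating | 3.3 | collected |
| A(c) moderate or severe | 3 | collected |
| A(d) aggravation | 3.2 | collected, but not limited to routine activity |
| A(d) avoidance | none | not collected |
| B nausea/vomiting, light, sound | 4 | collected |
| Medication | 3.5, "Did you take any medication to alleviate your head pain" | broader: any medication, where the definition says acute migraine medication |

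The nearest substitute for avoidance is item 5. It grades walking, moving the body and strenuous activity up to being unable to do them. It is not attributed to head pain, and the protocol does not map it to A(d). These entries also appear to belong to the seven-item Physical Function measure. Using them to score MMD would place content of the measure under test inside its own reference variable.

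**2. Find which days depend on avoidance.** Take a headache of qualifying duration and seven yes/no facts: unilateral, pulsating, moderate or severe, aggravation, avoidance, any B symptom, medication. That gives 2^7 = 128 patterns. Compare two rules:

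- as defined: (unilateral + pulsating + intensity + [aggravation or avoidance]) ≥ 2, or B, or medication;
- as the diary can score it: (unilateral + pulsating + intensity + aggravation) ≥ 2, or B, or medication.

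The rules differ in 3 of 128 patterns, each time from non-migraine to migraine day when avoidance is counted. In each, exactly one of the first three features is present, aggravation is No, avoidance is Yes, and there is no B symptom and no medication. The strenuous-exertion error works on the same narrow set of days, because A(d) decides the classification only there.

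**3. Illustrate the size.** The protocol gives no feature frequencies, so every input here is an assumption, with features taken as independent:

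share of headache days missed = P(exactly one of the three other A features) × P(no B) × P(no medication) × P(avoidance without reported worsening)

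Inputs: the three A features at 0.3 each, 0.5 each, or 0.6/0.6/0.7; any B symptom 0.3 to 0.8; medication 0.3 to 0.6; avoidance without reported worsening 0.02 to 0.20.

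- Smallest: P(exactly one) = 0.6×0.4×0.3 + 0.4×0.6×0.3 + 0.4×0.4×0.7 = 0.256. Then 0.256 × 0.2 × 0.4 × 0.02 = 0.0004, or 0.04%.
- Largest: P(exactly one) = 3×0.3×0.7×0.7 = 0.441. Then 0.441 × 0.7 × 0.7 × 0.20 = 0.043, or 4.3%.

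Per 12 headache days this is about 0.005 to 0.5 days. At the upper eligibility limit of 26 headache days per month (Section 6.1) it is about 0.01 to 1.1. The top end requires few A features, few B symptoms, little medication use and frequent avoidance all at once.

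**The case against.** The strongest reply is that the mismatch is real but hardly matters. Most days qualify by another route: two other A features, a single B symptom, or medication alone. Section 6.1 enrols people whose headaches show at least two pain features together with nausea, or with both light and sound sensitivity, which favours days that already qualify. It does not guarantee a B symptom on any given day. A participant who avoids activity because it hurts may also answer Yes to item 3.2, and the protocol holds no response data either way. MMD is one reference variable among several (MFIQ, MSQ, HIT-6, MOS-Cog-R, PGIS, PGIC), and item 2 separately records a self-reported migraine day. All of this stands and limits the size. None of it makes the avoidance part scorable.

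A reader might infer more than the documents support:

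- **That MMD is under-counted.** The avoidance gap alone can only lower the count. However, the unrestricted wording of item 3.2 and the any-medication wording of item 3.5 can both add days, so the net direction is not established.
- **That the missed days are the most disabling ones, weakening the relation between MMD and MiCOAS scores.** The affected days have one other A feature, no B symptom and no medication. Nothing in the protocol shows that function is worst on such days.
- **That a material loss can be quantified.** Assuming 1 to 3 dependent days per 28 and avoidance on 10 to 30% of them gives 0.1 to 0.9 days per month, but neither input comes from the protocol.

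**Conclusion.** The point holds as a minor inconsistency. Section 8.1.10 and Appendix C disagree on feature A(d): avoidance is in the definition but not in the diary, and item 3.2 is wider than routine activity. MMD as defined therefore cannot be computed from the data collected. The set of days on which this matters is narrow, at 3 of 128 patterns for the avoidance gap. The illustrative share missed, 0.04% to 4.3% of headache days, rests wholly on assumed frequencies and independence. The effect is probably small, and its true size and net direction cannot be determined from the protocol. The primary objective concerns the MiCOAS-7 and MiCOAS-14 items and scores, so it is touched only indirectly, through validation analyses that use MMD.

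**What to change.** Reconcile Appendix C with Section 8.1.10 in one of two ways.

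1. **Change the diary.** Word item 3.2 to cover pain that got worse with, or led the person to avoid, routine physical activity, with examples such as walking or climbing stairs. Alternatively, limit item 3.2 to routine activity and add a short conditional Yes/No item on avoidance because of head pain. The cost is a compound question in the first case and one more conditional item in the second. Item 3.2 appears to be one of the items added for MMD, so the MiCOAS-DA domain counts should not change.
2. **Change the definition.** If the diary is fixed, restate A(d) in Section 8.1.10 as what item 3.2 captures, and note that this departs from the definition the section presents as adapted from the headache classification and the FDA draft guidance. The cost is one line of text. MMD would then carry that stated departure wherever it is used as a reference variable.

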4.1 Aura was  ☐ Mild ☐ Moderate ☐ Severe
4.2 Dizziness or vertigo was  ☐ Mild ☐ Moderate ☐ Severe
4.3 Mental Slowness or Fogginess was  ☐ Mild ☐ Moderate ☐ Severe
4.4 Nausea was  ☐ Mild ☐ Moderate ☐ Severe
4.5 Neck Pain was  ☐ Mild ☐ Moderate ☐ Severe
4.6 Sensitivity to Light was  ☐ Mild ☐ Moderate ☐ Severe
